3. SUMMARY OF STUDY PLAN

3.1. Overview of Study and Study Design

We propose a double-blind, placebo-controlled randomized clinical trial of 40 mg of atorvastatin (Lipitor®) or placebo per day in 278 men and women age \geq 21 years old scheduled to receive Anthracycline-based chemotherapy for Stage I-III including inflammatory Breast Cancer, or lymphoma Stage I-IV with a $>$ 2 year life expectancy. Innovative noninvasive MRI measures of LV volumes, EF, myocardial strain, PWV, arterial wall thickness, and other serum markers plus key patient reported outcomes including cognition and quality of life measures will be collected at baseline, 6 and 24 months after initiating treatment with Anthracycline-based therapy. In addition, participants will be contacted by telephone to assess medication compliance/toxicities and Quality of Life at 12 and 18 months. Patients completing at least 24 months but no longer than 27 months of study medication will be followed for an additional 30 days after the last dose of study medication to evaluate any study related adverse events.

3.1.1 COVID-19 - Due to the inability to obtain a final 24 month assessment (related to social distancing because of Coronavirus) of the primary outcome measures for the Prevent study, this study has been amended to provide additional study drug to remaining participants for an additional 3 months. This provision extends the window of opportunity to collect the final study outcome measures within 27 months of beginning the study at a time when social distancing is not required due to the presence of the coronavirus in our communities. This amendment allows for final study related assessments to be accomplished with participants still receiving the study drug. Our statistical analyses which is ongoing to examine the change in outcomes over time allows the exact time between baseline and follow up to be accounted for (I.e. the exact number of days between visits). This modification to allow patients to have their final measurements after 24 months (I.e. 27 months) will not negatively impact our ability to evaluate the stated hypotheses and outcomes for this study. Moreover, this change we will ensure that to the best of our ability we will evaluate the efficacy of the study drug on patients who take the drug until their final outcome assessments, as was the intention of our trial.

3.2. We will use the established NCORP structure of the Wake Forest NCORP Research Base (WF NCORP RB). We will recruit from NCORP Community sites and/or NCI NCORP Research Bases with appropriate MRI facilities that treat modest numbers of breast cancer and lymphoma patients with Anthracycline-based therapy. Importantly, the PI has visited and conducted interviews with all participating NCORP Community sites and/or NCI NCORP Research Bases to verify their MRI and breast cancer and lymphoma recruitment capabilities.

3.3. MRI was selected to provide the endpoints of left ventricular volumes, LVEF, myocardial strain and PWV because of its:

- Reliability ($>$ 90% of the valuable subjects in the Jackson Heart Study for which [name] serves as the Co-PI of the core lab and the preliminary cancer studies mentioned in Section C.1.),
- Reproducibility ($<$ 2% discordance for repeated measures in the pilot data from the cancer participants),
- Accuracy (its ability to detect informative changes indicative of both CV disease and forecasting prognosis),
- Translational capability (its association with large NHLBI efforts to assess CV disease and thereby make additional comparisons), and

- Versatility (in that with a single imaging modality one cannot only collect information regarding the measurement of LVEF but also the factors such as pre-load and after-load that can also impact the measurement of LVEF).

Importantly, all sites have been verified as to the performance of these procedures via onsite interviews and case image recovery.

Ultrasound and radioisotope studies can be used to assess cardiac function. These measures, however, exhibit high variance, are operator-dependent, and are difficult to obtain in individuals with unfavorable body habitus. Radioisotope studies require exposure to ionizing radiation. Catheter-based assessments of left ventricular and vascular structure or function can be acquired but these techniques are associated with the risks of an interventional procedure. Thus, we selected MRI for this study.

4. PARTICIPANT SELECTION

4.1. Inclusion Criteria

- 4.1.1 Stage I-III breast cancer (including inflammatory and newly diagnosed recurrent breast cancer) or lymphoma Stage I-IV. **(Patients should have a > 2 year life expectancy)**
- 4.1.2 Scheduled to receive chemotherapy with an Anthracycline (doxorubicin or epirubicin)
- 4.1.3 ≥ 21 years of age
- 4.1.4 Patients that are receiving or have received chemotherapy regimens are allowed.
- 4.1.5 Prior administration of anthracyclines is acceptable if therapy was completed > 6 months prior to study enrollment.
- 4.1.6 Able to hold breath for 10 seconds
- 4.1.7 ECOG 0 or 1
- 4.1.8 See section 4.2.14 for new **exclusion** criteria for breast patients with tissue **expanders**.
- 4.1.9 Patients with breast **implants** are usually permitted to have an MRI. Check with the MRI technician to confirm.
- 4.1.10 Participants must have required labs (within 30 days prior to enrollment) as defined below:

It is recommended the Lipid Profile and Glucose be drawn Fasting ≥ 8 hrs.

- X Serum Lipid Profile: Total Cholesterol/HDL/LDL/Triglycerides
(LDL levels prior to chemotherapy must be ≤ 190 mg/dl)
- X Alanine aminotransferase level (ALT) ≤ 3 x ULN
- X Aspartate aminotransferase level (AST) ≤ 3 x ULN
- X Total bilirubin ≤ 2.0
- X TSH ≤ 1.5 times ULN
- X Creatine kinase ≤ 2.5 x the ULN
- X Glucose < 126 (Diabetics 40–75 years of age are not eligible, See 4.2.2)

If labs are drawn non-fasting and LDL levels are ≥ 190 mg/dl the Lipid Profile should be repeated fasting to determine eligibility. If glucose is ≥ 126 the glucose should be repeated fasting to determine eligibility.

4.2 Exclusion Criteria

- 4.2.1 Atherosclerotic cardiovascular disease (ASCVD) defined by history of acute coronary syndromes, MI, stable or unstable angina, coronary or other arterial revascularization, stroke, TIA, or peripheral arterial disease presumed to be of atherosclerotic origin.
- 4.2.2 40 to 75 years of age with diabetes per ACC/AHA 2013 Guidelines
- 4.2.3 Significant ventricular arrhythmias (>20 PVCs/min due to gating difficulty) atrial fibrillation with uncontrolled ventricular response
- 4.2.4 Current use of statin therapy
- 4.2.5 Current or history of hepatic dysfunction
- 4.2.6 Uncontrolled hypothyroidism
- 4.2.7 Recent extended history of constant-recurrent substance abuse or another medical condition that might compromise safety or the successful completion of the study.
- 4.2.8 Patients with ferromagnetic cerebral aneurysm clips or other intraorbital/intracranial metal; pacemakers, defibrillators, functioning neurostimulator devices or other implanted electronic devices.
- 4.2.9 Current use of the following CYP 3A4 inhibitors are not allowed: Boceprevir, Clarithromycin, Cyclosporine (oral), Darunavir plus ritonavir, Fosamprenavir, Fosamprenavir plus ritonavir, Gemfibrozil, Grapefruit juice >1 liter per day, Itraconazole, Lopinavir plus ritonavir, Nelfinavir, Saquinavir plus ritonavir, Telaprevir, Tipranavir plus ritonavir

- 4.2.10 Current use of Rifampin and Digoxin
- 4.2.11 Unable to provide informed consent
- 4.2.12 Symptomatic Claustrophobia
- 4.2.13 Pregnant or breast feeding. Due to unknown risks and potential harm to the unborn fetus a negative serum pregnancy test within 10 days prior to enrollment is required in women with child-bearing potential. For this reason women of child-bearing potential must agree to use adequate contraception (hormonal or barrier method of birth control; abstinence (not having sex), oral contraceptives, intrauterine device (IUD), DeProvera, tubal ligation, or vasectomy of the partner (with confirmed negative sperm counts) in a monogamous relationship (same partner). An acceptable, although less reliable method involves the careful use of condoms and spermicidal foam or gel and/or cervical cap or sponge prior to study entry and for the duration of study participation. Should a woman become pregnant or suspect she is pregnant while participating in this study, she should inform her study physician immediately.

Due to the potential effect of **atorvastatin** when excreted in breast milk, women who are currently breast-feeding are not eligible for this study.

- 4.2.14 Breast patients with tissue **expanders** are **not** allowed with the exception of tissue expanders made of material that are MRI compatible. Check with the MRI technician to confirm.

4.3. Inclusion of Women and Minorities

Table 2: Race/Ethnicity

Gender	White	Black or African-American	Hispanic or Latino	Asian or Pacific Islander	Unknown	Total
Male	30	8	0	0	0	38
Female	193	43	2	2	0	240
Total	223	51	2	2	0	278

4.4. Recruitment and Retention Plan

- 4.4.1 Over 600 breast and lymphoma patients should be eligible for enrollment among the NCORP sites, approximately 14% of whom will be males. Assuming conservatively that 17% (1 in 6) of the patients will consent to the study, we expect ~100 patients to be enrolled annually once the study is active at all planned sites. We will enroll 278 patients. We anticipate 28% of our cohort will drop out, so we expect 200 individuals to complete the study. In addition to NCORP sites, study enrollment will be opened to Alliance site members in which study coordinators, imaging expertise, and patient populations are readily available.
- 4.4.2. At each site, specific recruitment plans may include the following according to the site's institutional policy: screening clinic charts; tumor registry data; referral sources such as patient advocate groups, retirement communities, churches, support organizations, community organizations, newspapers, radio; or patient recruitment posters and recruitment letters.
- 4.4.3. The research PI or designee at each WF NCORP Research Base NCORP, which may include the clinic physician, resident, research nurse or research assistant, will review cancer registry and medical chart information to identify patients eligible for this protocol. Patients identified using these methods will be asked to join the study during their next clinic visit/consultation.

Accrual is expected to be 8 patients per month. Targeted accrual should be met in approximately 3 years for the 5 year study. A maximum of 278 patients will be enrolled on this trial. Patients will be followed for at least 24 months. Patients completing at least 24 months of study medication but no longer than 27 months will be followed for an additional 30 days after the last dose of study medication to evaluate any study related adverse events. After the Final assessment, the patient is no longer followed and data is no longer collected.

5. AGENT ADMINISTRATION

5.1. Dose Regimen and Dose Groups:

Group 1 (one 40 mg atorvastatin tablet each morning by mouth for at least 24 months but no longer than 27 months) and Group 2 (one placebo tablet each morning by mouth for at least 24 months but no longer than 27 months).

5.2. Atorvastatin/Placebo Administration

Patients will be 1:1 randomized to receive the study agent, (one 40 mg atorvastatin tablet daily by mouth for at least 24 months but no longer than 27 months) or a placebo (one tablet daily by mouth for at least 24 months but no longer than 27 months). The study agent or placebo should be started within 48 hours (2 days) prior to first chemotherapy treatment. The patient must receive 2 doses prior to first chemotherapy treatment. When possible those 2 doses may be given at least 12 hours apart. If necessary, due to time constraints, the patient may be given two tablets at the same time at least 90 minutes prior to first chemotherapy treatment.⁹⁸

Either agent will be taken once any time of day, with or without food, 7 days per week, on an outpatient basis, for a total of at least 24 months but no longer than 27 months. The atorvastatin pills and matching placebo pills used for this study will be provided free of charge to the patient.

5.3. Run-in Procedures. N/A

5.4. Contraindications

Active liver disease, which may include unexplained persistent elevations in hepatic transaminase levels, or hypersensitivity to any component of this medication.

5.5. Concomitant Medications

Atorvastatin is metabolized by cytochrome P450 3A4. Concomitant administration of this statin with inhibitors of CYP 3A4 can lead to increases in plasma concentrations of atorvastatin. The extent of interaction and potentiation of effects depend on the variability of effect on CYP 3A4. The following CYP 3A4 inhibitors are not allowed: Boceprevir, Clarithromycin, Cyclosporine (oral), Darunavir plus ritonavir, Fosamprenavir, Fosamprenavir plus ritonavir, Gemfibrozil, Grapefruit juice >1 liter per day, Itraconazole, Lopinavir plus ritonavir, Nelfinavir, Saquinavir plus ritonavir, Telaprevir, Tipranavir plus ritonavir. It is also recommended due to possible reactions to not use Rifampin and Digoxin.

5.6. Medication Modification

5.6.1 Medication Modification for Myalgias

Grade 1 Myalgias – If needed patient may take NSAIDs/analgesics at the discretion of the treating physician. Frequently this type of skeletal pain is not relieved with these medications.

Grade 2 or 3 Myalgias - Study medication should be held and patient instructed in the use of NSAIDs/analgesics per treating physician orders. ALT, AST and CK should be drawn within 24 hours.

- If labs are in acceptable range (ALT and AST are $< 3 \times \text{ULN}$ and CK $< 2.5 \times \text{ULN}$) study medication should be resumed.
- If Grade 2 or 3 myalgias redevelop, study medication should be discontinued. Patient will be considered off study medication but will continue to be followed.
- If ALT and/or AST are $> 3 \times \text{ULN}$ and/or CK $> 2.5 \times \text{ULN}$ study medication should be discontinued. Patient will be considered off study medication but will continue to be followed.

Any patient with suspected rhabdomyolysis/compartment syndrome of lower leg or rupture of tendon should stop the study medication immediately. The treating physician should assess the patient and order CK isoenzymes and/or other labs as deemed necessary. Patient will remain on study (off study medication) and be followed as usual.

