5.6.2.3 General Medication Modification

Contact [name] RN OCN at [contact] for any medication related issues. This includes but is not limited to the patient experiencing difficulty with their medication regimen due to chemotherapy treatment and delays or interruptions in taking study medication.

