5.7 Adherence

5.7.1 Adherence will be estimated as: 1) the proportion of expected pills taken while on treatment and 2) the proportion of the total number of pills that could be taken if the participant completed the study. We will calculate and report the mean adherence across all individuals as well as the proportion of patients who were 75% adherent (using both definitions of adherence). The primary analyses will include all randomized participants, regardless of adherence. Secondary analyses will be done using participants who were at least 75% adherent, separately using each definition.

5.7.2 To determine patients' adherence with the study agent, a medication diary will be utilized. It will be given to the patient by staff with instructions on how to complete. Every other month, medication diaries will be collected to verify medication usage. In addition, at 6 and 24

[figure not shown]
months any remaining bottle(s) of study agent will be collected from the patient and a pill count will be performed to verify the patient-recorded information in their medication diary.

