6.2 Reported Adverse Events and Potential Risks

Atorvastatin

Most Common Events

- **Gastrointestinal:** Abdominal pain (In pre-marketing and open extension studies with a median follow-up period of 18 months, abdominal pain was reported in 7.3% of enrolled patients [n=2423]), constipation (In pre-marketing and open extension studies with a median follow-up period of 18 months, constipation was reported in 6.6% of enrolled patients [n=2423]), nausea (In pre-marketing and open extension studies with a median follow-up period of 18 months, nausea was reported in 5.4% of enrolled patients [n=2423])
- **Neurologic:** Headache (In pre-marketing and open extension studies with a median follow-up period of 18 months, headache was reported in 7.4% of all patients enrolled [n=2423])
- **Respiratory:** Upper respiratory infection (9%)
- **Muscle Pain (Myalgia):** Soreness usually in upper arms and shoulders or hip and thighs about 6%.

Less Common

- Confusion < 2%

Rare but Serious Events

- **Hepatic:** Cholestatic hepatitis, increased liver enzymes (1%)
- **Musculoskeletal:** Compartment syndrome of lower leg, disorder of muscle (20 to 40 mg/day, 0.02% to 0.08%; 80 mg/day, 0.53% to 0.9%), rhabdomyolysis, rupture of tendon
- **Endocrine:** Diabetes < 0.25% or 1 per 400.

ProHance®

Most Common Events

- headache, nausea, vomiting, itching, watery eyes, skin rash, facial and/or tongue swelling,
- wheezing, chest tightness, or troubled breathing, hypotension (a decrease in blood pressure) may occur in about 2% of patients.

Less Common

- Extravasation happens in one out of every 250 to 500 procedures. <0.2 to 0.4%

Rare but Serious Events

- renal failure
- nephrogenic systemic fibrosis (NSF)
- confusion

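### Section 5.6.1 restarts study drug after Grade 2–3 myalgia on acceptable ALT, AST and CK alone, without requiring that the myalgia has improved

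*Combined protocol and SAP*

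**What the plan says.** Section 5.6.1 sets the steps for Grade 2 or 3 myalgia. First, "Study medication should be held and patient instructed in the use of NSAIDs/analgesics per treating physician orders". Next, "ALT, AST and CK should be drawn within 24 hours". If ALT and AST are below 3 times the upper limit of normal and CK is below 2.5 times, "study medication should be resumed".

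The section then gives three routes to stopping:

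- **Recurrence:** "If Grade 2 or 3 myalgias redevelop, study medication should be discontinued".
- **Labs:** discontinue if ALT, AST or CK is above those limits.
- **Suspected serious muscle or tendon injury:** stop at once for suspected rhabdomyolysis, compartment syndrome of the lower leg or tendon rupture.

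Three other places bear on the point. Section 5.6.2.2, on raised labs, has the site PI or treating physician review both labs and clinical status at 6 weeks and leaves rechallenge to that person's discretion. Section 5.6.2.3 names a study contact for medication problems, among them "delays or interruptions in taking study medication". Section 7.8 lists an adverse event among the reasons for which a participant may stop the drug.

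**The concern.** A symptom triggers the hold, but only a laboratory result releases it. The grade of pain that caused the drug to be withheld is not looked at again before restart. Under the grading in section 10.2, Grade 2 limits instrumental activities of daily living. Grade 3 is severe or medically significant and may be disabling or limit self-care. Section 5.6.1 itself remarks, under Grade 1, that this kind of pain often does not respond to NSAIDs or analgesics, so pain that persists through the hold is foreseeable.

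The main stake is patient safety: a patient still in Grade 2–3 pain may be put back on atorvastatin because the written condition has been met. A lesser stake is consistency. Sites that follow the text and sites that wait for improvement would treat the same patient differently. That alters drug exposure and could reach the secondary analyses restricted to participants with at least 75% adherence (sections 5.7.1 and 12.9).

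**Working it through.** The plan gives no figure to reproduce here. The check is a reading of the rule, followed by a rough sense of scale.

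**Following the rule for one patient.** Take a patient with Grade 2 or 3 myalgia that does not ease, and labs within the limits.

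1. Myalgia is Grade 2 or 3: hold the drug (5.6.1).
2. ALT, AST and CK are drawn and are in range: the resume condition is met. No grade, improvement or minimum hold is attached to it.
3. Recurrence stop: read literally, pain that never went away has not come back, so this stop is not reached.
4. Laboratory stop: not reached, because labs are in range.
5. Suspected rhabdomyolysis, compartment syndrome or tendon rupture: not reached if the myalgia is uncomplicated.

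Section 5.6.1 thus directs a restart and has no directed stop for this patient.

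**Looking for the missing condition elsewhere.**

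- 5.6.2.2 does ask for clinical status, but only on the path for raised labs.
- 5.6.2.3 gives a contact and no criterion.
- 6.9 (unblinding for toxicity) sets no condition for restarting.
- 7.8 is permissive and not specific to myalgia.

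None of these adds a symptom condition to the resume rule.

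**Scale.**

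- Patients per arm at 1:1 randomization (5.2, 12.1): 278 / 2 = 139.
- Myalgia rate on atorvastatin (6.2): about 6%.
- Atorvastatin patients with myalgia of any grade: 0.06 × 139 = 8.34, about 8.

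The share of these who would be Grade 2–3, within laboratory limits and not improved is not in the documents. As pure illustration, an assumed 10% gives 0.10 × 8.34 = 0.8 and an assumed 50% gives 0.50 × 8.34 = 4.2, so about 1 to 4 patients. This range carries no evidential weight. The documents give no myalgia rate during chemotherapy or on placebo, and placebo patients with myalgia follow the same blinded rule.

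**Effect on the analyses.** Section 5.7.1 states: "The primary analyses will include all randomized participants, regardless of adherence". Section 12.9 describes the primary set as randomized patients with at least one dose, and a patient whose drug is being held has already taken a dose. The patient is in the primary set on either description. For the adherence-based analyses, the second definition in 5.7.1 counts pills against the whole study. Missing more than 25% of 24 months means missing more than 0.25 × 24 = 6 months, so only a long hold or a permanent stop would by itself move an otherwise fully adherent patient below 75%.

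**The case against.** The best reply is that the rule, read in sequence, already assumes improvement. A stop for myalgia that comes back makes sense only if it had gone away, so the authors probably expected the pain to settle before restart. That is a fair reading of intent. It is still not a written condition, and the condition that is written is laboratory only.

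The second reply is that nobody is compelled to dose. A reader might infer from the text that restart is required within 24 hours, or that a site must keep a patient in pain on drug. The documents support neither inference. The 24 hours govern the blood draw, and no deadline is set for resuming. The treating physician is already involved through the analgesic orders, section 7.8 permits stopping for an adverse event, and section 5.6.2.3 offers a contact. These provisions soften the rule in practice. They leave the decision to judgement without giving a criterion, against an instruction that says the drug should be resumed.

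A reader might also infer that the protocol has no clinical stop for muscle harm apart from recurrence. That is wrong, because the separate stop for suspected rhabdomyolysis, compartment syndrome or tendon rupture does not wait for a laboratory result.

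There is other monitoring: telephone contacts at 12 and 18 months that ask about toxicities, nurse exams at 6 and 24–27 months, and six-monthly safety review. As for diaries, section 5.7.2 says: "Every other month, medication diaries will be collected to verify medication usage". It does not say that they record symptoms. All of this is too infrequent to stand in for a check at the moment of restart.

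Finally, a mandatory permanent stop for persistent pain could remove patients whose pain has nothing to do with study drug, including patients on placebo. That objection stands, and the remedy below avoids such a stop.

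**Conclusion.** The point holds as a minor patient-safety defect in one written rule. Confidence is high that the symptom condition is absent. The documents offer no evidence that harm or uneven site practice has followed, and none is claimed.

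The number of patients affected is probably small but cannot be derived; the figure of about 8 is only a reference for myalgia of any grade on atorvastatin, and is not an upper bound. The conclusion does not depend on it.

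It would be tempting to conclude that the primary LVEF comparison is compromised. The documents do not support that: the intention-to-treat set is the same whether or not the drug is restarted, and no sample size, power or alpha figure is touched. Any effect on the adherence-based secondary analyses is of unknown size and direction.

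**What to change.** Change the first bullet under Grade 2 or 3 myalgia in section 5.6.1 so that study drug is resumed only when ALT, AST and CK are in the acceptable range and the myalgia has improved to Grade 1 or less. If the labs are acceptable but the myalgia has not improved, keep the drug on hold. Leave any permanent discontinuation for persistent pain to the site PI's or treating physician's review of clinical status, following the model of section 5.6.2.2. Keep the existing stops for recurrence, raised labs and suspected serious muscle or tendon injury as they are.

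The cost is a symptom check when the laboratory results come back, repeated while the hold lasts, by telephone if need be. No scheduled visits, laboratory tests or patients are added. The downside is slightly less drug exposure in a small, uncountable number of patients, who stay in follow-up and in the primary analysis set.
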